4.8 Concomitant Medications/Treatments

4.8.1 Prohibited Medications

Over-the-counter soy-based foods, drinks, and supplements are not permitted for consumption during this study as they may confound study results. Any subject consuming soy-based food or supplements as part of his or her daily diet must discontinue consumption prior to taking protocol therapy on Cycle 1 Day 1. The study team will provide guidance to the subject to help determine whether his or her diet is consistent with this requirement of the study. **A subject handout summarizing prohibited food and drinks can be found in the Procedure Manual appendices.**

Soy consumption prior to and during treatment must be reported according to [Section 6.2](#) and [6.3](#). Consumption of prohibited soy products during the treatment period constitutes a protocol deviation and must be handled according to the Procedure Manual

and site IRB policy. Subjects will receive a “warning” and additional education for a first offense; ingestion a second time will result in discontinuation of protocol therapy ([Section 4.9](#)).

4.8.2 Concomitant Medications

For the purposes of this study, anti-neoplastic agents (i.e. chemotherapy, hormonal therapy, immunotherapy, other small molecule inhibitors, and gene therapy), antimicrobials (i.e. antibiotics, antifungals, antivirals), transfused blood products, G-CSF, and soy products will be the only collected concomitant medications. Antimicrobial agent use will be designated as prophylactic or for the treatment of a presumed or known infection. See [Section 6](#) for additional information about what data will be collected during the trial.

A platelet or packed red blood cell transfusion must be provided if any of the below criteria are met:

- Hemoglobin of < 7 g/dl or if symptomatic
- Platelets of < 10,000 cells/ μ l or abnormal bleeding
- Treating physician determines it is in the subject’s best clinical interest

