1.2 Background

1.2.1 Toxicities Associated With Chemotherapy for Pediatric Cancers

While cure rates for pediatric cancers have steadily improved over the last several decades, toxicities associated with cancer therapy continue to cause significant morbidity and mortality [1, 2]. Serious side effects of chemotherapy and radiation are common and are thought to be due to a variety of factors, including depletion of glutamine and glutathione, free radical generation, cytokine release, and oxidative damage [1, 3-9]. Unlike certain targeted anti-cancer agents, most chemotherapeutic drugs have nonspecific mechanisms of action that damage both normal tissue and cancer cells [1]. Similarly, the mechanism of action of radiation is nonspecific and can cause oxidative DNA damage to normal tissues that are within the radiation field [1]. These nonspecific effects of chemotherapy and radiation tend to be more severe in tissues that contain rapidly dividing, mitotically active cells such as those found in the bone marrow [1]. Myelosuppressive regimens cause a predictable decline in peripheral blood cell counts, usually 7 - 10 days after exposure to therapy. Highly-suppressed absolute neutrophil counts during this period put patients at an elevated risk for serious infection [10]. The standard of care at most institutions is to admit neutropenic patients with fever to the hospital and treat with empiric intravenous broad-spectrum antibiotics until their febrile neutropenia resolves. This is due to the high mortality associated with serious bacterial infections in this population, reported to be around 1% [11, 12]. Such patients also often require packed red blood cell and platelet transfusions for chemotherapy-induced anemia and thrombocytopenia, respectively, which are

associated with hemolytic transfusion reactions and transfusion-transmitted infections. Other common acute toxicities due to cancer treatment include mucositis caused by chemotherapy and radiation as well as neurotoxicity due to vincristine and other tubulin-inhibiting chemotherapeutic agents [13-15].

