3.1 Inclusion Criteria

- [1] Newly diagnosed solid tumor or lymphoma with histological verification
- [2] Age 1 - 21 years at time of diagnosis
- [3] Karnofsky/Lanksy performance score of ≥ 50
- [4] Able to tolerate enteral medication administration
- [5] Planned chemotherapeutic regimen for a patient must meet **all** of the following criteria:
 - a. A known myelosuppressive regimen which includes at least two of the following agents: actinomycin, carboplatin, cisplatin, cyclophosphamide, daunorubicin, doxorubicin, etoposide, ifosfamide, topotecan
 - b. At least four consecutive cycles
 - c. Cycle length is either 14 or 21 days
 - d. Regimen **must either alternate myelosuppressive chemotherapeutic agents in an X-Y-X-Y format**, such that the same chemotherapy is given every other cycle (e.g. vincristine/doxorubicin/cyclophosphamide | ifosfamide/etoposide), **or repeat the same chemotherapeutic agents each cycle in an X-X-X-X format** (e.g. repeated cycles of cisplatin/etoposide/bleomycin). Courses eligible for this trial may occur at any time during treatment provided that they are consecutive and follow the one of the described patterns. Non-myelosuppressive anti-neoplastic treatments will not be considered for the purposes of determining eligibility. Questions regarding whether or not a patient's chemotherapy plan meets inclusion criteria will be decided by the Study Chair.
- [6] Informed consent or parental permission and assent obtained prior to trial-related activities ([Section 4.3](#))
- [7] Able and willing to comply with all study related procedures
- [8] Women of childbearing potential must agree to use adequate contraception prior to study entry and for the duration of study participation. Should a woman become pregnant or suspect she is pregnant while participating in this study, she should inform her treating physician immediately.

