4.7 Dosage and Administration

4.7.1 Chemotherapeutic Regimen

The chemotherapeutic regimen must meet the inclusion criteria described in [Section 3.1](#). Administration of anti-neoplastic therapy must follow standard clinical practices, including dosing delays and dose modifications to anti-neoplastic therapy. See [Section 4.7.3](#) for information pertaining to treatment delays.

If the pre-treatment audiogram for subjects scheduled to receive platinum-based chemotherapy is indicative of severe hearing loss, the chemotherapeutic dose should be adjusted according to standard clinical practices. Any change(s) to the anticipated cancer treatment regimen must be captured in OnCore.

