6 EVALUATIONS AND ASSESSMENTS

6.1 Study Procedures and Assessments Table

Table 3: Schedule of Events

Assessment ¹	Pre-Treatment	Treatment Phase				Follow-up ²
	Day -28 to Day 1 ³	Cycle 1 Day 1 ^{3,4}	Cycles 1 - 4 Weekly ⁵	Cycles 2 - 4 Day 1	Cycle 4 Last Day ⁶	
Informed Consent	X					
Eligibility Determination	X					
Baseline ⁷ and Demographic ⁸ Data	X					
Randomization ⁹	X					
Medical History/Baseline Condition	X					
Physical Exam ¹⁰	X	X	X	X		
Height and Weight		X		X		
Chemistry/Metabolic Panel ¹¹	X	X		X		
CBC with Differential ¹²	X		X	X		
CRP, ESR, and Homocysteine ¹³	X			X	X	
Cytokine and Isoflavone Panels ¹⁴		X		X	X	
Audiogram ¹⁵	X			X	X	
Concomitant Medications Review ¹⁶	X ¹⁷	X	X	X	X	
Adverse Events Review		X	X	X	X	X
Study Medication Dispensing		X		X		
Subject Pill Diary ¹⁸		X	X	X	X	
Study Medication Reconciliation				X	X	

¹ All visits and assessments must be completed within ± 72 hours of the milestone date unless otherwise specified.

² Subjects must be followed for 30 days following the last study intervention for AEs and for 6 months for SAEs, unless consent is withdrawn.

³ Cycles begin on Day 1. There is no Day 0.

⁴ Cycle 1 Day 1 assessments do not need to be repeated if completed in the 7 days prior (i.e. Day -7 to Day 1) unless otherwise stated.

⁵ Weekly visits are to occur at 7-day intervals between Day 1 and the cycle's last day.

⁶ The last day of a cycle corresponds to the Day 1 of the next cycle. The last day's number will vary by cycle length.

⁷ Diagnosis, stage, grade, site(s) of disease, anti-neoplastic treatment +/- radiation regimen

⁸ Age, sex, race, and ethnicity

⁹ Randomization must occur within the 2 days prior to the anticipated Cycle 1 Day 1. ([Section 4.5](#))

¹⁰ Full physical exam at the beginning of each cycle of chemotherapy, and a symptom-directed physical exam at each of the weekly treatment visits. Collect height, weight and BSA on Day 1 of each cycle.

¹¹ Chemistry labs to assess for general safety must be conducted on Day 1 of each cycle. They must include serum creatinine, total bilirubin, AST, and ALT.

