6.2 Pre-treatment Assessments

Informed consent will be obtained from a parent or guardian of eligible minor subjects, or the patient if ≥ 18 years old. Oral assent will be obtained from minor subjects ≥ 7 years old, unless more stringent requirements are imposed by a site's IRB. Consent and assent must be obtained prior to any study-related procedures. ([Section 4.3](#), Procedure Manual)

Subject eligibility must be confirmed prior to subject enrollment using the inclusion and exclusion criteria ([Section 3.1](#) – [3.2](#)). The following data must also be collected pre-treatment:

- Clinical data: diagnosis, stage, grade, site(s) of disease
 - Stage (extent of spread): *in situ*, localized, regional, distant, unknown
 - Grade (differentiation level): well differentiated/low grade, moderately differentiated/moderate grade, poorly differentiated/high grade, undifferentiated/highest grade
- Anticipated anti-neoplastic treatment regimen for courses coinciding with this trial: therapeutic agents (i.e. chemotherapy, hormonal therapy, immunotherapy, other small molecule inhibitors, gene therapy), doses expressed per kilogram body weight, duration of cycle (14 or 21 days), radiation dose and number of fractions (if applicable)
- Demographic data: date of birth, sex, race, and ethnicity
- Blood sample collection for serum homocysteine, C-reactive protein (CRP), and erythrocyte sedimentation rate (ESR), and complete blood count (CBC) with differential must be drawn at baseline (Day -7 to Day 1). Raw data will be reported.
 - CBC with differential must include hemoglobin, hematocrit, platelet count, total white blood cell count and automated white blood cell differential (manual differential if automated not available) (Procedure Manual).
- Medical history and physical exam for the purpose of establishing baseline conditions ([Section 6.2.1](#))
- Audiogram on Day -7 to Day 1 for subjects receiving platinum-based chemotherapy
- Use of the following concomitant medications in the 28 days prior to the anticipated Cycle 1 Day 1: G-CSF, antimicrobials, blood product transfusions, anti-neoplastic agents, and soy-based products. See [Sections 4.8](#), [6.3](#), and the Procedure Manual for additional details on concomitant medications.

In addition, the following **target AEs** must be assessed during the Pre-treatment Period. Use assessment closest to Cycle 1 Day 1 if more than one assessment is done during the Pre-treatment period.

- Neutropenia

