8.4 Data Analyses Plans

Graphical and repeated measure models will be used to describe the complete pattern of ANC over all four cycles. Between-group (Cycles 1 & 2) and crossover differences (Cycles 1 - 4) form the structure for treatment comparisons. Repeated measure models

will be used to assess differences in raw ANC, daily ANC, days with fever, duration of hospitalization, and duration of antimicrobial use for subjects admitted with febrile neutropenia. The Cochran–Mantel–Haenszel test statistics will be used in the analysis of stratified categorical data such as neutropenia grades (severe: ≤ 100 cells/ μl ; moderate: ≤ 500 cells/ μl ; mild: ≤ 1000 cells/ μl) and filgrastim (G-CSF) usage. For duration and severity of mucositis and peripheral motor neuropathy, detailed physical examinations will be documented at each weekly physical exam. Grading (grade 1 - 5) will be performed according to the [CTCAE](#) guidelines, version 4.0. The Cochran–Mantel–Haenszel test will be used to compare grade and repeated measure models for duration of mucositis between cycles containing genistein versus placebo.

Number of subjects who experience hearing impairment and tinnitus will be summarized by treatment for each cycle. The number of required blood product transfusions, both packed red blood cells and platelets, will be documented and compared during genistein and placebo cycles using repeated measure models. Reporting will be in the form of total ml/kg body weight infused of red blood cells and platelets. Criteria for transfusion are listed in [Section 4.8.2](#).

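### Radiotherapy during study cycles is not recorded by date, field or cycle, which leaves avoidable noise in the genistein–placebo comparison, mainly for oral mucositis

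*Combined protocol and SAP*

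**What the plan says.** **Radiotherapy is expected and not barred.** Baseline data in the Section 6.1 schedule include "anti-neoplastic treatment +/- radiation regimen". Section 6.2 asks, within the anticipated regimen for the study cycles, for "radiation dose and number of fractions (if applicable". No rule in Sections 3.2, 4.8.1 or 4.9 excludes radiotherapy or stops study treatment because of it.

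**Matching and stratification do not involve it.** Criterion 5d in Section 3.1 requires the chemotherapy to repeat every cycle or every other cycle. Section 8.3 stratifies by cycle length only.

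**Recording during treatment.** Section 4.8.2 says that anti-neoplastic agents, antimicrobials, "transfused blood products, G-CSF, and soy products will be the only collected concomitant medications". It defines "anti-neoplastic agents (i.e. chemotherapy, hormonal therapy, immunotherapy, other small molecule inhibitors, and gene therapy", with no mention of radiation. The per-cycle list in Section 6.3 covers supplement intake, delays and dose reductions, admissions, antimicrobials, transfusions, G-CSF and soy. Radiation is not on it. Section 4.7.1 adds that "Any change(s) to the anticipated cancer treatment regimen must be captured in OnCore", without tying a change to a cycle.

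**Relevance by the protocol's own account.** Section 1.2.1 names "mucositis caused by chemotherapy and radiation" among common acute toxicities, and says the effects of both treatments tend to be worse in rapidly dividing tissue such as marrow. It limits radiation damage to tissue inside the field.

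**Analysis.** Section 8.1 has two co-primary endpoints: (a) mean recovery day over Cycles 1 and 2, compared between arms, and (b) the within-subject difference between genistein and placebo cycles. Section 8.4 plans "repeated measure models for duration of mucositis between cycles containing genistein versus placebo" and names no radiotherapy term.

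**The concern.** The crossover depends on genistein and placebo cycles being alike apart from the supplement. Criterion 5d secures this for chemotherapy. Radiotherapy given in only one of the two periods breaks the likeness. If it falls in Cycles 3–4 only, it lies in the placebo cycles of an Arm A subject and in the genistein cycles of an Arm B subject, so the two subjects' differences move in opposite directions.

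Across arms this cancels in expectation. In 44 subjects it need not cancel exactly, and it widens the spread of the differences in any case. Because the protocol asks for neither dates nor field, the planned dataset would not show which cycles were affected, and no planned analysis takes them into account.

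Oral mucositis is the most exposed endpoint, because the protocol itself names radiation as a cause, although only tissue in the field is affected. Neutrophil recovery is exposed to the extent that substantial marrow is irradiated.

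**Working it through.** **1. The plan's own figures.** Inputs from Section 8.2: Poisson means 16.25 and 13.25, 22 per arm, one-sided 5% Mann-Whitney-Wilcoxon test. Simulation with 20,000 samples gives 79.7% power with continuity correction and 80.1% without, against the stated 80% or so. Accrual is 44 / 0.90 = 48.9, rounded up to 49. Both figures reproduce and are not in question.

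**2. Assumptions.** The documents give no radiotherapy frequency and no effect on recovery. Let a share f of subjects be affected, with recovery shifted by d days. The range examined is f = 10–40% and d = 1–5 days.

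**3. Size of a chance imbalance in recovery day.**
- Between arms, radiation in the compared cycles: SD = d × √(2f(1−f)/22). For f = 0.1, d = 1 this is √(0.18/22) = 0.09 days. For f = 0.3, d = 3 it is 3 × √(0.42/22) = 0.41 days. For f = 0.4, d = 5 it is 5 × √(0.48/22) = 0.74 days.
- Pooled crossover difference, radiation in Cycles 3–4 only: with kA and kB affected subjects in Arms A and B, the shift is d × (kB − kA)/44, with SD d × √(44f(1−f))/44. For f = 0.1, d = 1 this is √3.96/44 = 0.05 days. For f = 0.3, d = 3 it is 3 × √9.24/44 = 0.21 days. For f = 0.4, d = 5 it is 5 × √10.56/44 = 0.37 days.
- A 2 versus 6 split with d = 3 shifts the pooled difference by 3 × 4/44 = 0.27 days. A 4 versus 4 split shifts it by 0.

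All of these are small against the 3-day target.

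**4. Power in the Section 8.2 set-up** (one Poisson draw per subject, radiation in the compared cycles, both arms alike):

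| Affected | Shift | Power |
|---|---|---|
| none | – | 79.7% |
| 10% | 1 / 2 / 3 days | 80.3 / 78.8 / 78.2% |
| 20% | 1 / 2 / 3 days | 79.8 / 77.5 / 76.4% |
| 30% | 1 / 2 / 3 days | 79.6 / 78.2 / 75.3% |
| 20–40% | 3–5 days | 76% down to 66% |

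The loss runs from about 0 to 79.7 − 66 ≈ 14 points. At shifts of 1–2 days it is about 0–2 points, close to simulation error.

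**5. Co-primary (a) as defined.** Section 8.1 averages two cycles, whereas step 4 uses one draw. With two-cycle averages and independent cycles, power is 96.9% with no radiotherapy, 94.0% at f = 20%, d = 3, and 82.2% at f = 40%, d = 5. Correlation between a subject's cycles would reduce this gain.

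**6. Co-primary (b).** Radiation in the second period only, period-adjusted t-test on two-cycle averages, independent cycles. At a 3-day effect, power stays above 99% throughout. At a 1.5-day effect, which the protocol does not specify, it falls from 80% to 76–68% for f = 30–40% and d = 3–5.

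**7. Mucositis.** The documents give no mucositis rate or duration, so no figure can be attached to the endpoint most exposed.

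**The case against.** Four points are strong, and most of them stand.

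- **A reader might infer that affected cycles can never be identified.** The documents do not support that. Planned dose and fractions are collected (Section 6.2), regimen changes are captured (Section 4.7.1), source records are retained (Section 11.3), and sample case report forms sit in a Procedure Manual not reproduced here (Section 10.1). Dates could probably be recovered later. What stands is that the protocol does not ask for them and no prespecified analysis uses them.
- **A reader might infer that the protocol expressly waives radiotherapy from cycle matching.** Section 4.8.2 is about medications and refers to Section 6 for what is collected, so radiation's absence from that list alone shows little. The criterion 5d sentence "Non-myelosuppressive anti-neoplastic treatments will not be considered for the purposes of determining eligibility" does not clearly reach a treatment that can suppress marrow. The point rests on 5d matching chemotherapeutic agents only, and on Section 6.3 having no radiation item.
- **Field.** Radiation away from the mouth and from substantial marrow need not affect either endpoint, and nothing in the documents supports a shift as large as 3–5 days. The chart review behind the 16.25-day mean is not said to exclude irradiated patients, so adding days to it may count some of the effect twice.
- **Scenario.** Radiation in Cycles 3–4 only cannot affect (a). The losses in step 4 need it in Cycles 1–2.

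These points limit the size of the concern. They do not remove the recording gap.

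**Conclusion.** The concern holds as a minor, inexpensive improvement. Radiotherapy in the study cycles is implicitly allowed, lies outside the chemotherapy matching, and is recorded as a plan and as changes to the plan, not by date, field or cycle.

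A reader might infer bias in favour of genistein or against it. The documents do not support that: the sequence is randomised 1:1 and blinded, so radiotherapy timing is balanced in expectation. What remains is added variance and chance imbalance, which unequal drop-out between arms could enlarge.

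For the primary endpoints the effect is modest. It is about 0 to 14 points of power in the single-draw set-up under the assumed ranges. With two-cycle averages, (a) stays above about 80% and the loss for (b) at 3 days is negligible, both assuming independent cycles. The main exposure is oral mucositis when the mouth is in the field, and its size cannot be computed from the documents. No stated figure in the plan is wrong on this account.

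**What to change.** 1. **Section 6.2:** before randomisation, record the study cycles in which radiation is planned, and the planned field.
2. **Section 6.3, per-cycle report:** add radiation start and stop dates and field, taken from the existing treatment record.
3. **Section 8.4:** in the repeated-measures models for recovery day, ANC and mucositis, include a per-cycle indicator of planned concurrent radiation. Because the plan is fixed before randomisation, treatment cannot affect it.
4. **Section 8.4:** add a sensitivity analysis that omits matched cycle pairs (1 with 3, 2 with 4) in which only one cycle had radiation. This pairing suits both chemotherapy patterns in 5d. It uses delivered radiation, known only after randomisation, so it is supportive only.

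The cost is one CRF item and one degree of freedom. In simulation the covariate cost almost nothing when the shift was 1–2 days and restored nearly all the lost power when it was 3–5 days. Eligibility, treatment and sample size do not change.

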4.9 Discontinuation of Protocol Therapy

Subjects will receive genistein or placebo for four 14- or 21-day cycles of chemotherapy, depending upon chemotherapeutic regimen, or until any of the following occur:

- Development of a secondary condition which, in the investigator’s opinion, would compromise patient safety or study results
- A female subject becomes pregnant
- Non-compliance with study procedures or protocol therapy (missing more than 20% of prescribed doses of genistein/placebo) since the first dose of study supplement treatment
- Consumption of prohibited soy-based products more than once during the Treatment Phase ([Section 4.8.1](#))
- Unacceptable AE(s). Subjects who experience [National Cancer Institute \(NCI\) Common Terminology Criteria for Adverse Events \(CTCAE\) Version 4](#) grade 3 or higher AE that is possibly, probably, or definitely related to the genistein/placebo during Cycle 3 or 4
- Chemotherapy regimen is altered such that it no longer meets Inclusion Criterion #5 ([Section 3.1](#))
- Subject’s treatment assignment is unblinded ([Section 4.6](#))
- Subject decides to discontinue protocol therapy

If a subject discontinues protocol therapy for any of the above reasons, the subject will be considered “Off-treatment” and the subject will be “On Follow-Up”. Subjects removed

from protocol therapy for (an) unacceptable AE(s) will be followed until resolution or stabilization of the AE.

Should a pregnant subject consent, the subject will also be followed to determine the outcome of her pregnancy (including any premature termination of the pregnancy). Generally, follow-up will be requested by the Sponsor no longer than 8 weeks following the delivery or termination date.

